7.6 Demographic and Other Baseline Characteristics

Demographic, medical history and other clinically relevant baseline variables will be summarized by treatment using descriptive statistics (i.e., number of observations available, mean, standard deviation, minimum, and maximum for continuous variables and counts and percentages for qualitative variables).

7.7 Treatment Characteristics

Index procedure and post-procedural characteristics and results will be summarized using general methodology as described in Section 7.2.

7.8 Interim Analyses

No interim analysis is planned for the randomized studies or single arm VLU study.

7.9 Evaluation of Objectives

VenaSeal vs. Surgical Stripping

2 primary endpoints and 2 key secondary endpoints will be evaluated.

VenaSeal vs. ETA

3 primary endpoints and 2 key secondary endpoints will be evaluated.

VLU Single Arm Study

No hypothesis testing will be done.

7.9.1 Randomized Studies

7.9.1.1 Analysis of Primary Endpoints

7.9.1.1.1 Hypothesis

For Primary endpoints of VenousTSQe at 30 days and VenousTSQs at 30 days, the following hypothesis will be tested:

$$H_0: p_A = p_C$$

$$H_a: p_A \neq p_C$$

Where p_A and p_C are the true PROM scale for the VenaSeal™ system arm and ETA or surgical stripping arm, respectively.

To compare the percentage of target vein length successfully treated between treatment and control, the following hypothesis will be tested:

$$H_0: \mu_A = \mu_C$$
$$H_a: \mu_A \neq \mu_C$$

Where μ_A and μ_C are the percentage of reflux treated at the index procedure for the VenaSeal™ system arm and ETA.

7.9.1.1.2 Endpoint Definition

The VenaSeal vs. ETA Randomized Study has three primary endpoints comparing the VenaSeal™ system to ETA.

1. *Peri-procedural patient satisfaction* as measured by a validated, patient-centered venous treatment satisfaction questionnaire (VenousTSQe) at 30 days post index-procedure.
2. *Overall patient satisfaction* as measured by a validated, patient-centered venous treatment satisfaction questionnaire (VenousTSQs) at 30 days post index-procedure.
3. Elimination of clinically relevant superficial truncal disease in each target vein at the time of index procedure as measured by the percentage of target vein length successfully treated.

The VenaSeal vs. Surgical Stripping Randomized Study has three primary endpoints comparing the VenaSeal™ system to Surgical Stripping.

1. *Peri-procedural patient satisfaction* as measured by a validated, patient-centered venous treatment satisfaction questionnaire (VenousTSQe) at 30 days post index-procedure.
2. *Overall patient satisfaction* as measured by a validated, patient-centered venous treatment satisfaction questionnaire (VenousTSQs) at 30 days post index-procedure.
3. Elimination of clinically relevant superficial truncal disease in each target vein at the time of index procedure as measured by the percentage of target vein length successfully treated will be summarized but no statistical hypothesis testing will be done.

7.9.1.1.3 Rationale for Performance Criteria

If the null hypothesis is rejected, it demonstrates that the treatment satisfaction or percentage of the target vein successfully treated with the VenaSeal™ system is significantly different from the treatment with ETA or surgical stripping.

When the two-sided P-value is less than the pre-specified critical value alpha per adjustment of multiple comparison (described in Section 7.5) and the mean of certain primary endpoint in treatment with VenaSeal™ is greater than that in control of ETA or Surgical Stripping, the superiority of treatment with VenaSeal™ on that primary endpoint can be declared.

7.9.1.1.4 Analysis Methods

VenousTSQe and VenousTSQs consist of 8 and 11 items, respectively, with each item having the possibility to be scored from 0-6. The scores will be collected from eCRFs at 30 days.

The VenousTSQe score is calculated as:

Item 1 (from the VenousTSQs) + Item 2 + Item 4 + Item 5b + Item 6b + Item 7

Items 1, 3, and 8 from the VenousTSQe are not used.

Since the VenousTSQe score is the sum of 6 items, it can range from 0 to 36.

The Venous TSQs score is calculated as:

Item 1 + Item 2 + Item 4b + Item 6 + Item 7b + Item 9

Items 3, 5, 8, 10 and 11 are not used.

Since the VenousTSQs is the sum of 6 items, it can range from 0 to 36.

Scoring Notes

Some items included in the scores are skipped when they are not applicable, based on a previous question. For example, consider 5a and 5b in the VenousTSQe

5a asks: "Immediately after the procedure, did you wear compression stockings or bandages?" If the response to 5a is "no", 5b is skipped. 5b asks "How bothered were you by wearing compression stockings / bandages?", so it doesn't apply if no stockings / bandages were worn. In these cases, when an item in the score is skipped because of a response to the prior, related question, it will be scored as 6. For item 5b, 6 indicates "not bothered at all", which is sensible, since a person cannot be bothered by stockings that are not worn.

If the follow-up question is supposed to be skipped, but is not, the follow-up response will be used only if it is consistent with the prior, related question. If 5a is marked "no" (indicating that stockings were not worn), and 5b is not skipped, then:

- If 5b = 5 or 5b = 6, 5b will be used to calculate the score.
- If 5b < 5, then the responses are inconsistent, and 5b will be considered missing.

If a prior question is marked "yes", but the follow-up question is left blank, then the item will be considered missing:

- If 5a is marked "yes", but 5b is missing, then 5b will be considered missing.

Calculating the Score When Items are Missing

The VenousTSQe and VenousTSQs scores are missing when any of the included items is missing.

Hypothesis Test of the TSQ

(Shapiro-Wilk test) Normality on the outcomes of primary endpoints of PROM scores and % of target vein length successfully treated will be checked in each treatment arm first.

If one of the treatment arms is not normal for a primary endpoint ($p < 0.05$), Wilcoxon rank-sum test will be used in the comparison between VenaSeal™ arm and control arm (ETA or Surgical Stripping). The test

statistic can be calculated by $Z = \frac{|R_1 - \mu_{R_1}| - 0.5}{\sigma_{R_1}}$ using normal approximation with 0.5 continuity correction, where R_1 is the summary of rank of PROM scores in treatment (VenaSeal) arm, μ_{R_1} is the expectation of R_1 and $\sigma_{R_1}^2$ is the variance of R_1 . Null hypothesis can be rejected if $|Z| > Z_{\alpha/2}$ and P value can be calculated by $1 - \Phi(Z)$.

If both treatment arms are normal for a primary endpoint, Two-sample T test will be used in the comparison between VenaSeal™ arm and control arm (ETA or Surgical Stripping). Null hypothesis can be rejected if the test statistic t has $|t| > t_{\frac{\alpha}{2}, N-1}$. If the Equality of Variances output has a p value ≥ 0.05 , the “pooled” variance will be computed as the weighted average of the sample variances; if the Equality of Variances output has a p value < 0.05 , the “Satterthwaite” will be computed as the weighted average of the sample variances.

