7.9.1.1.6 Sensitivity and Missing Data Analysis

It is recommended to perform an additional scoring of the TSQe that does not include Item 5, i.e. the Compression stockings question.

To account for missing data in the primary endpoint evaluation, two forms of imputation will be performed. For patients that have no baseline information collected, they will be assigned the average value of the TSQ in the control arm. For patients with a baseline visit and baseline information collected, multiple imputation will be performed as a sensitivity analysis. Subjects who do not obtain their VenousTSQe at 30 days, VenousTSQs at 30 days or the percentage of target vein treated at procedure will have these measurements imputed using PROC MI in SAS. The covariates to be used in the imputation model are age, gender, race, diabetes, CEAP classification, Historical Superficial and Deep Venous Treatment, Family History of Chronic Venous Disease, VCSS at baseline, 7 days and 30 days, Length of clinically relevant superficial truncal disease in target vein and treatment arms. Ten imputed data sets will be generated using regression method (REG option in PROC MI). The overall PROM scores for VenousTSQe and VenousTSQs and % target vein treated success and their standard errors will be generated for each of ten imputed data sets. PROC MIANALYZE in SAS will be used to summarize the overall treatment difference, standard error, and two-sided 95% confidence interval.

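### For a primary endpoint tested by Wilcoxon, the SAP takes the p-value from ranks but the direction of superiority from means, so VenaSeal can be declared superior on a rank test that favours control

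*SAP*

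**What the plan says.** SAP 7.9.1.1.4 runs a Shapiro-Wilk test on the trial's own outcome data, separately by arm: "Normality on the outcomes of primary endpoints of PROM scores and % of target vein length successfully treated will be checked". When at least one arm gives p < 0.05, the "Wilcoxon rank-sum test will be used in the comparison between VenaSeal™ arm and control arm". Otherwise: "If both treatment arms are normal for a primary endpoint, Two-sample T test will be used in the comparison". Inside the t branch a second pretest, beginning "If the Equality of Variances output has a p value", picks pooled or Satterthwaite variance. The Wilcoxon statistic is built from the absolute deviation of the rank sum from its expectation, so its sign is lost.

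SAP 7.9.1.1.3 then allows superiority to be declared when the two-sided p-value is below the adjusted alpha and "the mean of certain primary endpoint in treatment with VenaSeal™ is greater than that in control of ETA or Surgical Stripping". This applies whichever test supplied the p-value. Neither section requires the ranks and the means to point the same way.

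The surrounding plan works with mean differences. SAP 6.1.1 and protocol 14.1.1 size the primaries with a t test on a difference and an SD. SAP 7.9.1.1.6 reports the imputed-data sensitivity analysis as a difference: "PROC MIANALYZE in SAS will be used to summarize the overall treatment difference, standard error, and two-sided 95% confidence interval".

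**The concern.** A rank-sum test asks whether a randomly chosen patient in one arm tends to score higher than one in the other. A mean comparison asks which average is higher. Under a simple shift the two agree. If one arm has more patients at the ceiling but also a deeper tail of poor results, they can disagree: the ranks favour that arm and the mean favours the other.

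The protocol gives reason to expect such a shape for elimination of truncal disease. Its treatment outcome groups (section 9.2, Table 5) separate complete treatment from incomplete treatment in which the full vein length was not treated. That suggests many values at 100% and a shortfall tail that may differ by modality.

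The stake is a confirmatory claim. A primary declared successful this way counts in the Hochberg steps of SAP 7.5 and releases alpha to the key secondary endpoints.

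**Working it through.** **1. The plan's own sizing.** Inputs from SAP 6.1.1: difference 0.5 SD (5 points with SD 10, or 10% with SD 20%), two-sided alpha 0.0167, power 90%, 1:1 allocation.

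- Per arm, n = 2(z₁₋α/₂ + z₁₋β)² / 0.5² = 8 × (2.393 + 1.282)² ≈ 108.0, so 109 by the normal approximation.
- Exact noncentral t: 89.9% power at 109 and 90.2% at 110, so 110 per arm is right.
- Attrition: 220 / 0.93 = 236.6, so 237 for TSQ; 220 / 0.97 = 226.8, so 227 for elimination.

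The figures reproduce, and they are figures for a test on means.

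**2. How ranks and means part.** The documents give no outcome distribution, so these examples are assumptions. They also assume that percentage treated cannot exceed 100, which the SAP does not state.

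*Example A.* VenaSeal: 65% at 100, 35% near 85. Control: 80% at 100, 20% near 40.
- Means: 0.65×100 + 0.35×85 = 94.75, against 0.80×100 + 0.20×40 = 88.0. VenaSeal is higher.
- Pairs: control higher 0.80×0.35 = 0.28; VenaSeal higher 0.20; tied 0.80×0.65 = 0.52. Splitting ties gives control 0.54 and VenaSeal 0.46. The ranks favour control.

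*Example B.* VenaSeal: 40% at 100, the rest uniform on 75 to 99. Control: 75% at 100, the rest uniform on 40 to 80.
- Means: 0.40×100 + 0.60×87 = 92.2, against 0.75×100 + 0.25×60 = 90.0. VenaSeal is higher.
- Pairs, ignoring the small overlap of the tails: control higher 0.75×0.60 = 0.45; VenaSeal higher 0.25; tied 0.30. Control 0.60, VenaSeal 0.40.

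**3. How often the rule then contradicts itself.** The SAP rule was simulated with a two-sided p-value, counting trials in which VenaSeal is declared superior while the ranks favour control. For A, 264 × 0.97 ≈ 256, or 128 per arm. Wilcoxon was selected in 100% of trials in A, B and B with the deeper tail.

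| Scenario | Per arm | Alpha | Contradiction |
|---|---|---|---|
| A (shortfall SD 5 and 10) | 128 | 0.05 | 28% |
| A | 128 | 0.025 | 20% |
| A | 128 | 0.0167 | 17% |
| A with a milder control tail | 128 | 0.0167 to 0.05 | about 2% to 10% |
| B | 110 | 0.0167 | 56% |
| B with control tail 20 to 80 | 110 | 0.0167 | 64% |

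In B a t test on the means rejects in only about 8% of trials, so the SAP would usually claim superiority on the mean without evidence from a mean comparison. Close variants of B gave 66% to 77%, with a Welch test supporting VenaSeal in 9% to 19%.

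**4. TSQ scores.** Assumed 0 to 36 scores, SD 6, 110 per arm:

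- Wilcoxon was chosen in 28%, 37%, 96% and 100% of trials at means of 18, 20, 24 and 28. Other ways of generating scores with a mean near 24 gave 24% and 54%, so these rates are illustrative only.
- When the arms were identically distributed, two-stage type I error was 0.012 to 0.020 against 0.0167.
- No contradiction occurred under the null or a 3-point shift, nor in a scenario where only stocking use differed (20% against 90%). In that last scenario Wilcoxon was chosen in 98% of trials at 110 per arm and 53% at 50 per arm, so the same endpoint could be tested differently in the two randomized studies.

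**The case against.** The strongest reply is that the algorithm is complete: test, threshold, both branches, variance option and direction are all written down, and nothing is left to the analyst. That is correct. A reader might infer that the confirmatory analysis is open to choice after the fact, or that pretesting inflates the error rate. The documents do not support the first, and the simulations under identical distributions do not support the second.

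It is also fair to say that SAP 7.9.1.1.1 does not call its parameters means. It speaks of the PROM scale and the percentage of reflux treated, so a rank test does not contradict the hypotheses as worded. Only the sizing, the direction clause and the imputation summary are tied to mean differences, and the SAP labels the multiple imputation a sensitivity analysis.

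Example A is a constructed case. Its arms have SDs of about 7 and 24, where the SAP assumes a common 20%, and nothing in the documents says that a fifth of controls would have only about 40% of the vein treated. The 28% needs alpha 0.05, which Hochberg allows only if all three primary p-values fall below it. In that example the true mean does favour VenaSeal, and a Welch test declares it superior in 89% of simulated trials, so A shows incoherence more than a false claim. Example B shows the worse case, where the mean evidence is weak and the rule still declares superiority.

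What survives is that a stated rule can join a p-value for one quantity to the sign of another, and no text prevents it.

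**Conclusion.** The rule is wrong as written for the Wilcoxon branch. The mismatch is certain from the text. How often it would lead to a contradictory claim is not known: from about 2% to over 70% of trials, depending on the tails and the alpha level, all under assumed distributions and only where the arms differ in shape.

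It matters most for percentage of vein length treated, and only in the ETA study, because the Surgical Stripping Study summarises that endpoint without a test. A reader might extend the contradiction to all three primaries and both studies. The TSQ scenarios examined do not show it. For TSQ the remaining point is smaller: which quantity is tested may vary with the data and between studies.

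Sample size is not affected.

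**What to change.** Delete the normality pretest from SAP 7.9.1.1.4 and name one test for each primary, with the direction and the estimate taken from that same test. A Welch-type comparison of means, reported as a difference with its 95% CI, fits the sizing, the direction rule in 7.9.1.1.3 and the imputation summary in 7.9.1.1.6. It also makes the variance pretest unnecessary. Keep the rank test as a sensitivity analysis.

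At minimum, if Wilcoxon is retained, amend 7.9.1.1.3 so that direction is read from the rank statistic.

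The cost is SAP wording only: 110 evaluable per arm still gives about 90% power under the plan's assumptions, and 237 in total stands. Adjusting for the randomisation strata is a separate, optional choice.

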10.4. Randomization and Treatment Assignment (CEAP 2-5)

After a patient has signed the ICF, the CEAP assessment has been completed, and the eligibility criteria are verified, the patient will be enrolled via randomization. There are two Randomized Studies:

1. VenaSeal vs. ETA Study: subjects will be 1:1 randomized to VenaSeal™ system or ETA treatment.
2. VenaSeal vs. Surgical Stripping Study: subjects were randomized 1:1 to VenaSeal™ system or surgical stripping treatment. VenaSeal vs Surgical Stripping Study was closed to enrollment as of 22-Feb-2022.

Each site will be designated as participating in only one of the two Randomized Studies and cannot participate in both. Which study the site will enroll into is pre-determined by geographical region and device/treatment availability (i.e., regulatory approval and reimbursable status). Randomization will be accomplished using the Oracle Clinical system (or paper back-up if the system is down) prior to the collection of Baseline visit data and will be stratified by the site and by CEAP (2004) clinical category to ensure balanced arms. Site personnel will obtain the subject's randomization sequence on the Randomization CRF which will be generated from the database. Randomization schedules will be prepared for each site using a random permuted block design stratified by site and CEAP (2004) (grouping categories 2-3 vs. 4-5).

If a subject is inadvertently randomized twice or more, the first assigned treatment arm will be used for the intention-to-treat analysis, and investigators should treat subjects according to the first randomization. Knowledge of the development of randomization lists may lead to selection bias, therefore these details will be described in a separate document. If a subject is inadvertently treated with the wrong treatment modality, this will be recorded as a protocol deviation.

Randomization may be done during the screening visit as applicable or may be completed closer to the Baseline visit if there will be a significant delay between Screening and Baseline.

CEAP 6, active VLU subjects will not be randomized and will be treated with the VenaSeal™ system.

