5.1 Study Design

The study design is a global, post-market, prospective, multi-center, randomized-controlled study of patients with symptomatic superficial venous disease, with a single-arm embedded ulcer group. The study is designed with two Randomized Studies (VenaSeal vs. Surgical Stripping Study and VenaSeal vs. ETA Study) for CEAP 2-5 subjects and one single arm active VLU Study for CEAP 6 subjects. Each study will be individually assessed and analyzed for the overall study objectives.

There will be approximately 500 subjects enrolled in the VenaSeal Spectrum Study. Approximately 375 subjects will be enrolled in CEAP clinical classifications 2-5 in the Randomized Studies (108 subjects in VenaSeal vs. Surgical Stripping Study and about 264 subjects in VenaSeal vs. ETA Study), and up to 125 CEAP 6 subjects with VLUs will be treated with the VenaSeal™ system.

Enrollment of the VenaSeal vs. Surgical Stripping Study was closed on 22-Feb-2022. All subjects participating in the VenaSeal vs ETA Study or in the VLU Study (CEAP 2-6) will be followed up to 60 months post-index procedure, all subjects participating in the VenaSeal vs. Surgical Stripping Study will be followed up to 12 months post-index procedure.

Enrollment will take place at up to 40 sites globally.

To avoid introduction of bias to the study results due to disproportionate enrollment, enrollment at any individual site shall not exceed 20% of any single study (approximately 50 subjects for the Randomized Studies and 25 subjects for the VLU Study, excluding screen failures) of the total sample size. It is expected that sites enroll a minimum of 10 subjects per individual study the site is participating in. Enrollment was halted early for the VenaSeal vs. Surgical Stripping study, so control of each site's contribution to the overall total was not possible.

Randomization will be stratified by study site and CEAP classification 2/3 vs. 4/5. There is no blinding in this study. The detailed procedure of randomization information is described in the Randomization and Blinding Plan separately.

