7.3 Center Pooling

For each study, data will be pooled across sites for analysis. Results will be also summarized and presented for primary and key secondary endpoints by site for each study.

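### Randomisation is stratified by site and CEAP group, but the primary tests use neither factor; if either predicts satisfaction, the tests are conservative and give up modest power

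*SAP*

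**What the plan says.** Protocol 10.4 has randomisation "stratified by the site and by CEAP (2004) clinical category to ensure balanced arms", using permuted blocks with CEAP grouped 2-3 vs 4-5. SAP 5.1 agrees: "Randomization will be stratified by study site and CEAP classification 2/3 vs. 4/5".

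For the primary endpoints, SAP 7.9.1.1.4 applies a Shapiro-Wilk check in each arm. If either arm fails, a "Wilcoxon rank-sum test will be used in the comparison between" the two arms; if both pass, a two-sample t test. Neither contains site or CEAP. SAP 7.3 adds: "For each study, data will be pooled across sites for analysis", with by-site results as summaries only.

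CEAP enters the primary endpoints only through the multiple-imputation sensitivity analysis in 7.9.1.1.6: "The covariates to be used in the imputation model are age, gender, race, diabetes, CEAP classification". Site is not in that list. No stratified or covariate-adjusted comparison of the primary endpoints is planned, even as a sensitivity analysis.

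The decision rule in 7.9.1.1.3 is two-sided: "When the two-sided P-value is less than the pre-specified critical value alpha per adjustment of multiple comparison", with direction judged on the means.

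**The concern.** Stratified blocking removes most between-stratum imbalance from the treatment difference. An unadjusted test still counts between-stratum variation as noise, so its standard error is too large. If site or CEAP predicts the outcome, the test rejects a true null less often than its nominal level and has less power than the design could deliver. If neither predicts it, nothing is lost.

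The stripping study is where this matters. SAP 5.1 records that "Enrollment was halted early for the VenaSeal vs. Surgical Stripping study", and it closed at 108 subjects against 237 calculated (SAP 6.1.3). Analysis efficiency is one of the few levers left there.

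The return-to-work and closure tests are also unstratified, but no claim is made about them here.

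**Working it through.** **Inputs from the documents.** Difference 0.5 points per item; SD 1 point per item, so the standardised effect is 0.5; two-sided alpha 0.0167 for sample size; 7% attrition; 1:1 allocation (SAP 6.1.1). Six scored items: "Since the VenousTSQe score is the sum of 6 items, it can range from 0 to 36" (SAP 7.9.1.1.4), so the difference is 3 points with SD 6. Evaluable numbers: 108 × 0.93 = 100 (stripping) and 264 × 0.93 = 246 (ETA).

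**The plan's own figure.** With 110 per arm, the non-centrality is 0.5 × √(110/2) = 3.708 and the critical value is 2.393. Power = Φ(3.708 − 2.393) = 90.6% (90.2% by the exact t test). 220/0.93 = 237. The figure reproduces.

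**Closed form.** Let R² be the share of outcome variance explained by site and CEAP (assumed; not in the documents), with balance within strata taken as perfect:

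- unadjusted type I error = 2[1 − Φ(z/√(1−R²))]
- unadjusted power = Φ((ncp − z)/√(1−R²))
- adjusted power = Φ(ncp/√(1−R²) − z)

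| Case | R² | Type I, unadjusted | Power, unadjusted | Power, adjusted |
|---|---|---|---|---|
| 110 per arm, alpha 0.0167 | 0.10 | 0.0116 | 91.7% | 93.5% |
| 110 per arm, alpha 0.0167 | 0.20 | 0.0075 | 92.9% | 96.0% |
| 50 per arm, alpha 0.025 | 0.10 | 0.0181 | 60.7% | 65.3% |
| 50 per arm, alpha 0.025 | 0.20 | 0.0122 | 61.4% | 71.0% |

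**Simulation of the rank branch.** Real blocks are incomplete and scores are bounded, so gains are smaller than the closed form. Assumed: blocks of 4 within site × CEAP; 30% in CEAP 4-5; random dropout; scores 28 + 6z rounded and held to 0-36; stripping with 10 sites, of 10-11 subjects or from 26 down to 2; ETA with 24 sites of 11, or 20 sites from 50 down to 1. There were 4,000 runs per power row. Shapiro-Wilk sent 94-100% of the checked power runs to the rank branch. The comparison is unadjusted Wilcoxon → model on ranks with CEAP fixed and site random:

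| Site ICC | Stripping, equal sites | Stripping, unequal | ETA, equal | ETA, unequal |
|---|---|---|---|---|
| 0 | 55.1 → 55.9 | 54.9 → 56.0 | 91.5 → 91.8 | 91.6 → 91.8 |
| 0.03 | 55.5 → 57.2 | 54.0 → 55.7 | 92.2 → 92.5 | 91.8 → 92.5 |
| 0.10 | 56.6 → 60.9 | 55.3 → 59.1 | 92.9 → 94.7 | 92.8 → 94.1 |
| 0.20 | 56.8 → 65.2 | 56.9 → 65.2 | 93.1 → 96.1 | 93.3 → 96.1 |

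(Power in %; alpha 0.025 for stripping, 0.0167 for ETA.)

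With no strata effect the model already reads 0.8-1.2 points higher in stripping, because it has no continuity correction and a slightly higher error rate. Net of that, the gain due to strata in stripping is about 0.5-0.9 points at ICC 0.03, 3 at 0.10 and 7-8 at 0.20.

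**Type I error, stripping, nominal 0.025.** Wilcoxon: 0.022-0.023, 0.019-0.022 and 0.017 at ICC 0.03, 0.10 and 0.20. Model: 0.025-0.028.

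**Other settings, stripping, gross gain over ICC 0.03-0.20.** Alpha 0.05: 0.7-6.0 points. With the SAP's less conservative SD of 0.75 per item: 1.0-4.8 at alpha 0.025 and 0.6-3.0 at 0.05.

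**CEAP alone.** With an assumed 0.3 SD shift and 30% in CEAP 4-5, R² = 0.3 × 0.7 × 0.3² = 0.019. The gain is about 0.3 points in ETA and about 1 in stripping.

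**Alternatives.** A van Elteren test by site × CEAP cell cut stripping power from 55.3% to 45.5% at ICC 0. Fixed site effects on ranks cost about 1 point when sites do not differ (54.1% vs 55.1%; 54.0% vs 54.9%).

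**The case against.** The strongest reply is that a valid, conservative test is a permissible choice and that the benefit rests on assumptions: ICC, site sizes, block size, CEAP mix and control mean. That stands. It is why this is an efficiency point, and why the gain at ICC 0.03, or from CEAP alone, is about a point or less.

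A second reply is that the stripping figures use an unfavourable case. The SAP calls its SD an overestimate, and the cited six-item SDs are 3.56 and 5.04 against the 6 used here. At 50 per arm and alpha 0.025, t-test power would be about 97% and 76%, and the closed-form gain at R² 0.10 would be 0.5 and 3.4 points. Also, alpha 0.025 binds only when the other satisfaction endpoint misses 0.05. Both facts are right and shrink the gain; neither reverses it.

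A third is that the model may be slightly anti-conservative: with no strata effect its type I error in stripping was 0.027-0.029 at nominal 0.025, against 0.025-0.027 for Wilcoxon. This comes from a normal reference distribution (0.027-0.030). With the ordinary mixed-model t reference, a further simulation gave 0.024-0.027, with stripping power still rising from 56% to 61% at ICC 0.10.

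Last, the trial is open-label and stripping enrolment closed in February 2022, so a late change could look data-driven. That is a fair constraint on timing, and the fix depends on it.

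**Conclusion.** The concern holds. The strata used to randomise are absent from the primary tests, and under the two-sided rule the consequence is conservatism and not inflated error. The planned 90% power in the ETA study is intact: the gain there is 0.4-3.0 points over ICC 0.03-0.20. In the stripping study the gross gain is 1.7-8.5 points over the same range at alpha 0.025 and SD equal to the number of items, of which about 3 points at ICC 0.10 are due to the strata.

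All of this is conditional on a site effect that the documents neither give nor exclude. CEAP is the only stratification factor that the SAP itself treats as a possible predictor, and alone it is worth about 1 point at most. Confidence in the direction is high; confidence in the size is moderate. The change is worth making because it is cheap.

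**What to change.** Before the comparative analysis, amend SAP 7.9.1.1.4:

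- Compare VenousTSQe and VenousTSQs with a linear model containing treatment, CEAP group (2-3 vs 4-5) and site as a random effect, dropped if its variance is estimated as zero. Use a t reference, not a normal one.
- Keep the Shapiro-Wilk rule; where it selects the rank branch, fit the same model to the ranks. Judge direction on the means, as 7.9.1.1.3 already does.
- In the ETA study, if truncal disease elimination is analysed per vein, add a subject random effect. No calculation was run for that endpoint.
- Report the unadjusted t and Wilcoxon tests as sensitivity analyses. Do not use van Elteren by site-by-CEAP cell.
- Leave the return-to-work and closure tests as the confirmatory analyses; CEAP-stratified versions are optional sensitivity analyses.

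Separately, 7.9.1.1.4 gives a one-tailed formula, 1 − Φ(Z), for the Wilcoxon p-value. It must be reconciled with the two-sided rule in 7.9.1.1.3, because the conservatism described here assumes a two-sided p-value.

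The cost is SAP wording, minor programming and a recorded justification under SAP 7.12. With no strata effect the model lost no power in simulation; allow up to about 1 point. If comparative results have already been seen, the adjusted model should be reported as a sensitivity analysis only.
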